## Medtronic Controlled Information

This document is electronically controlled

056-F275, v A Clinical Investigation Plan Template

## 1. Investigator Statement

Participating investigators will be provided with a separate investigator agreement to document their obligations and commitment with respect to study conduct.

## 2. Glossary

Term	Definition
ADE	Adverse Device Effect
Advanced Evaluation	A tined lead is surgically implanted and externalized via a percutaneous extension for test stimulation.
AE	Adverse Event
Basic Evaluation	A temporary test stimulation lead is surgically implanted, externalized and connected to a patient cable for test stimulation.
CCIS	Cleveland Clinic Incontinence Score
CFR	Code of Federal Regulations
CI	Confidence Interval
CIP	Clinical Investigational Plan
CISC	Clean Intermittent Self-Catheterization
eCRF	Electronic Case Report Form
EC	Ethics Committee
EU	Europe
FI	Fecal Incontinence
—	—
GCP	Good Clinical Practice
HIPAA	Health Insurance Portability and Accountability Act
HRQL	Health Related Quality of Life
ICF	Informed Consent Form
OAB-q	Overactive Bladder Symptoms Quality of Life Questionnaire
IDE	Investigational Device Exemption

Term	Definition
IRB	Institutional Review Board
MedDRA	Medical Dictionary for Regulatory Activities
MI	Multiple Imputation
NOUR	Non-Obstructive Urinary Retention
OAB	Overactive Bladder
[REDACTED]	[REDACTED]
PMCF	Post-Market Clinical Follow-up
Oracle RDC	Oracle Remote Data Capture
QoL	Quality of Life
SADE	Serious Adverse Device Effect
SAE	Serious Adverse Event
SAP	Statistical Analysis Plan
SNM	Sacral Neuromodulation
US	United States
UF	Urgency Frequency
UI	Urinary Incontinence
UUI	Urinary Urge Incontinence

### 3. Synopsis

Title	Evaluation of InterStim Micro System Performance and Safety (ELITE) Post Market Clinical Follow-Up Study to Confirm Long-Term Outcomes
Clinical Study Type	Prospective, Multicenter, Global, Single-arm, Open-label, Post-market
Product Name	This post-market clinical follow-up (PMCF) will include the following commercially approved products: 

▪ InterStim Micro implantable neurostimulator

▪ InterStim SureScan MRI tined lead

▪ Patient and clinician therapy application software

▪ Wireless recharger

▪ Recharger application software

▪ Percutaneous extension (advanced therapy evaluation)

▪ Temporary lead (basic therapy evaluation)

▪ Verify external neurostimulator

Sponsor	Medtronic, Inc.
Indication under investigation	The indications under investigation are overactive bladder, fecal incontinence, and non-obstructive urinary retention. Refer to geography-specific labeling for additional details on indications.  There are no investigational devices used in this study, all study products will be used in accordance with the product labeling.
Investigation Purpose	Post-market clinical follow-up to confirm long-term safety and performance of the InterStim Micro System for sacral neuromodulation.
Overactive Bladder (OAB) Cohort Objectives	
Primary Objective:
 

• To demonstrate an improvement in Overactive Bladder Quality of Life (OAB-q) Questionnaire Health Related Quality of Life (HRQL) total score at 3 months post-implant compared to baseline

 
Additional Measures:
 

• [REDACTED]

• [REDACTED]

• [REDACTED]

• [REDACTED]

• [REDACTED]

• [REDACTED]

• [REDACTED]

• [REDACTED]

Fecal Incontinence (FI) Cohort Objectives	
Primary Objective:
 

• To demonstrate an improvement in Cleveland Clinic Incontinence Score (CCIS) at 3 months post-implant compared to baseline

 
Additional Measures:
 

• [REDACTED]

• [REDACTED]

• [REDACTED]

• [REDACTED]

• [REDACTED]

• [REDACTED]

• [REDACTED]

• [REDACTED]

Non-Obstructive Urinary Retention (NOUR) Cohort Objectives	
Primary Objectives:
 

• To demonstrate an improvement in number of clean intermittent self-catheterizations (CISC) per day at 3 months post-implant compared to baseline

 
Additional Measures:
 

• [REDACTED]

• [REDACTED]

• [REDACTED]

• [REDACTED]

• [REDACTED]

• [REDACTED]

• [REDACTED]

• [REDACTED]

Safety Assessment	To characterize safety of the InterStim Micro System by summarizing the adverse device effects and serious adverse device effects during the study. Safety measures will be summarized for each cohort as well as pooled for all patients regardless of indication. Device deficiencies will also be collected and reported.

Study Design	
This is a prospective, multicenter, global, single-arm, open-label, post market clinical follow-up study to characterize long-term clinical performance and safety of the InterStim Micro system. The study is intended to be conducted at approximately 40 centers in the United States (and United States Territories), Europe, Australia and Canada.
 
Eligible subjects, who are already candidates for sacral neuromodulation, will sign a study-specific informed consent form (ICF). Each subject will only be qualified for one of the study cohorts. Subjects will complete a Baseline Visit, a Lead Placement visit, Neurostimulator Device Implant visit and Three-month, Six-month, One-year, and Two-year Follow-up Visits. All subjects who met all eligibility criteria and complete the neurostimulator implant procedure will be considered enrolled in the study.

Sample Size	Approximately 160 subjects (60 for overactive bladder cohort, 60 for fecal incontinence cohort and 40 for non-obstructive urinary retention cohort), will be enrolled in the study to achieve a minimum of 50 evaluable implanted subjects each for overactive bladder and fecal incontinence cohorts and a minimum of 30 evaluable implanted subjects for non-obstructive urinary retention cohort at 3 months post implant.

**Overactive Bladder (OAB) -  
Cohort Eligibility Criteria**Inclusion Criteria:

1. Have a diagnosis of OAB as demonstrated on a 3-day voiding diary with greater than or equal to 8 urgency frequency episodes per day and/or by having a minimum of 3 episodes of urinary urge incontinence in 72 hours
2. Subjects 18 years of age or older
3. Candidate for sacral neuromodulation therapy in accordance with the InterStim Micro System labeling
4. Willing and able to accurately complete study diaries, questionnaires, attend visits, device recharging and comply with the study protocol
5. Willing and able to provide signed and dated informed consent

Exclusion Criteria:

1. Have neurological conditions such as multiple sclerosis, clinically significant peripheral neuropathy or spinal cord injury (e.g., paraplegia)
2. Have primary stress incontinence or mixed incontinence where the stress component overrides the urge component
3. Current urinary tract mechanical obstruction (e.g. benign prostatic enlargement or urethral stricture)
4. Have had treatment of urinary symptoms with botulinum toxin therapy in the past 12 months
5. Have knowledge of planned shortwave diathermy, microwave diathermy, or therapeutic diathermy
6. Women who are pregnant or planning to become pregnant
7. Characteristics indicating a poor understanding of the study or characteristics that indicate the subject may have poor compliance with the study protocol requirements.
8. Concurrent participation in another clinical study that may add additional safety risks and/or confound study results.\*

\*Subjects in concurrent studies can only be enrolled with permission from Medtronic. Contact Medtronic's study manager to determine if the subject can be enrolled in both studies.

**Fecal Incontinence (FI) –  
Cohort Eligibility Criteria**Inclusion Criteria:

1. Have a diagnosis of fecal incontinence as demonstrated by a 7-day bowel diary as greater than or equal to 2 incontinent episodes of more than staining (i.e., either slight, moderate or severe soiling)
2. Subjects 18 years of age or older
3. Candidate for sacral neuromodulation therapy in accordance with the InterStim Micro System labeling
4. Willing and able to accurately complete study diaries, questionnaires, attend visits, device recharging and comply with the study protocol
5. Willing and able to provide signed and dated informed consent

Exclusion Criteria:

1. Have neurological conditions such as multiple sclerosis, clinically significant peripheral neuropathy or spinal cord injury (e.g., paraplegia)
2. Uncorrected high grade internal rectal prolapse
3. Have knowledge of planned shortwave diathermy, microwave diathermy, or therapeutic diathermy
4. Women who are pregnant or planning to become pregnant
5. Characteristics indicating a poor understanding of the study or characteristics that indicate the subject may have poor compliance with the study protocol requirements.
6. Concurrent participation in another clinical study that may add additional safety risks and/or confound study results.\*

\*Subjects in concurrent studies can only be enrolled with permission from Medtronic. Contact Medtronic's study manager to determine if the subject can be enrolled in both studies

**Non-Obstructive Urinary Retention (NOUR) – Cohort Eligibility Criteria**Inclusion Criteria:

1. Have a diagnosis of non-obstructive urinary retention as demonstrated by a 7-day urinary voiding diary with a minimum of 5 clean intermittent self-catheterizations
2. Chronic non-obstructive urinary retention with an elevated post-void residual (PVR) that has persisted for at least six months and is documented on two or more separate occasions.
3. Subjects 18 years of age or older
4. Candidate for sacral neuromodulation therapy in accordance with the InterStim Micro System labeling
5. Willing and able to accurately complete study diaries, questionnaires, attend visits, device recharging and comply with the study protocol
6. Willing and able to provide signed and dated informed consent

Exclusion Criteria:

1. Have neurological conditions such as multiple sclerosis, clinically significant peripheral neuropathy or spinal cord injury (e.g., paraplegia)
2. Current urinary tract mechanical obstruction (e.g. benign prostatic enlargement or urethral stricture)
3. Have knowledge of planned shortwave diathermy, microwave diathermy, or therapeutic diathermy .
4. Women who are pregnant or planning to become pregnant
5. Characteristics indicating a poor understanding of the study or characteristics that indicate the subject may have poor compliance with the study protocol requirements.
6. Concurrent participation in another clinical study that may add additional safety risks and/or confound study results.\*

\*Subjects in concurrent studies can only be enrolled with permission from Medtronic. Contact Medtronic's study manager to determine if the subject can be enrolled in both studies.

Study Procedures and Assessments	Study Visits: 

1. Baseline Visit

2. Evaluation Lead Implant Visit

3. Tined lead (if applicable) / Neurostimulator Device Implant

4. Three-month Follow-up Visit

5. Six-month Follow-up Visit

6. One-year Follow-up Visit

7. Two-year Follow-up Visit

 
Baseline Each subject must meet all the inclusion and no exclusion criteria of one of the three study cohorts to be eligible to participate in the study. At the baseline visit, data will be gathered from subjects [REDACTED] [REDACTED]
 
For subjects who qualify with the overactive bladder indication: The urinary voiding diary will be explained and given to the subject to be completed for 3 consecutive days. The diary must be completed along with confirmation that the subject is not pregnant or planning to become pregnant as part of the assessment for study eligibility (female subjects of child bearing potential only). The Overactive Bladder Quality of Life (OAB-q) questionnaire will be collected.
 
For subjects who qualify with the fecal incontinence indication: The bowel diary will be explained and given to the subject to be completed for 7 consecutive days. The diary must be completed along with confirmation that the subject is not pregnant or planning to become pregnant as part of the assessment for study eligibility (female subjects of child bearing potential only). The Cleveland Clinic Incontinence Score (CCIS) [REDACTED] will be collected.
 
For subjects who qualify with the non-obstructive urinary retention indication: The urinary voiding diary will be explained and given to the subject to be completed for 7 consecutive days. The diary must be completed, collection of baseline post-void residual volume and confirmation that the subject is not pregnant or planning to become pregnant as part of the assessment for study eligibility (female subjects of child bearing potential only). [REDACTED] [REDACTED] [REDACTED]

----------------------------------	---

**Evaluation Lead Implant:**

If using basic evaluation, the basic evaluation lead should be placed in accordance with the device implant manual. [REDACTED]

If using advanced evaluation, the tined lead should be placed in accordance with the device implant manual. [REDACTED]

For both advanced and basic evaluation, throughout the study, unilateral stimulation is required. Programming may be set per Investigator discretion for the duration of the study. Any [REDACTED] reportable adverse events/device deficiencies will be documented and reported.

**Therapy Evaluation**

The therapy evaluation period should be conducted in accordance with the labeling using the Verify® external neurostimulator and should not exceed the therapy evaluation duration for the specific geography.

A study diary will be completed towards the end of the therapy evaluation period (completed for 3 consecutive days for overactive bladder, completed for 7 consecutive days for fecal incontinence and for non-obstructive urinary retention). Therapeutic success must be achieved in order to qualify for a neurostimulator implant in the study.

Any [REDACTED] reportable adverse events/device deficiencies will be documented and reported. [REDACTED]

**Tined lead (if applicable) / Neurostimulator Device Implant**

Once the subject qualifies for the neurostimulator device implant, site personnel may proceed with the Neurostimulator Device Implant Visit. If a subject does not qualify for the neurostimulator device implant, they will be exited from the study.

For subjects who qualify for neurostimulator device implant following a successful basic evaluation, the tined lead should be placed in accordance with the device implant manual. [REDACTED]

---

**Medtronic Controlled Information**

[REDACTED]. The neurostimulator should be implanted in accordance with the device's implant manual.

For subjects who qualify for neurostimulator device implant following a successful advanced evaluation, the neurostimulator should be implanted in accordance with the device's implant manual.

[REDACTED]  
[REDACTED]  
[REDACTED]

Any [REDACTED] reportable adverse events/device deficiencies will be documented and reported. [REDACTED]  
[REDACTED]  
[REDACTED]

### Three-month, Six-month, One-year, and Two-year Follow-up Visits

For subjects within the overactive bladder cohort:

[REDACTED] The Overactive Bladder  
Quality of Life (OAB-q), [REDACTED]  
[REDACTED] will be collected.

For subjects within the fecal incontinence cohort:

[REDACTED] The Cleveland Clinic  
Incontinence Score (CCIS), [REDACTED]  
[REDACTED] will be collected.

For subjects within the non-obstructive urinary retention cohort:

The voiding diary will be given to the subject to be completed for 7 days approximately 1 week prior to each follow-up visit. [REDACTED]  
[REDACTED]  
[REDACTED]

	
For all subjects, [REDACTED] reportable adverse events/device deficiencies will be documented and reported. [REDACTED] [REDACTED]
 
Unscheduled Visit An unscheduled visit may be needed for any device-related reason. During the visit, [REDACTED] reportable adverse events and/or device deficiencies will be collected. [REDACTED] [REDACTED]
 
Surgical Revision A surgical revision may be needed for replacement, revision or explant of the tined lead, neurostimulator or both. During the visit, [REDACTED] reportable adverse events and/or device deficiencies will be collected. [REDACTED] [REDACTED]

Statistics	
For the overactive bladder cohort, the primary objective is to demonstrate an improvement of Overactive Bladder Quality of Life (OAB-q) Questionnaire Health Related Quality of Life (HRQL) score at 3 months post-implant compared to baseline. A sample size of 50 achieves greater than 90% power to detect a difference from baseline of 30 points in Overactive Bladder Quality of Life (OAB-q) Questionnaire Health Related Quality of Life (HRQL) total score and a standard deviation of 27 with a significance level of 0.05 using a two-sided one sample t-test.
 
For the fecal incontinence cohort, the primary objective is to demonstrate an improvement in Cleveland Clinic Incontinence Score (CCIS) at 3 months post-implant compared to baseline. A sample size of 50 achieves greater than 90% power to detect a difference from baseline of 5 points in Cleveland Clinic Incontinence Score (CCIS) and a standard deviation of 6 with a significance level of 0.05 using a two-sided one sample t-test.
 
For the non-obstructive urinary retention cohort, the primary objective is to demonstrate an improvement in number of clean intermittent self-catheterizations (CISC) per day at 3 months post-

implant compared to baseline. A sample size of 30 achieves greater than 90% power to detect a difference from baseline of 2 clean intermittent self-catheterizations (CISC)/day and a standard deviation of 3 with a significance level of 0.05 using a two-sided one sample t-test.

To accommodate attritions, approximately 160 subjects (60 for overactive bladder cohort, 60 for fecal incontinence cohort and 40 for non-obstructive urinary retention cohort), will be enrolled in the study to achieve a minimum of 50 evaluable subjects each for overactive bladder and fecal incontinence cohorts and a minimum of 30 evaluable implanted subjects for non-obstructive urinary retention cohort at 3 months post implant.

For the primary objective in each cohort, the analysis on the change of primary outcome parameter at 3 months from baseline will be performed on subjects who provide complete data at baseline and 3 months. A two-sided one sample t-test, or Wilcoxon Singed Rank test will be performed to test the hypothesis depending on data normality.

Adverse events and device deficiencies of all cohorts will be summarized using summary tables displaying the frequency and percentages. Adverse events will be summarized by seriousness as well.

## 4. Introduction

### 4.1. Background

Sacral Neuromodulation (SNM) is a treatment for bladder and bowel control symptoms through the modulation of sacral nerves. SNM is delivered by sending electrical pulses to the sacral nerve to modulate the neural activity that influences the behavior of the pelvic floor, lower urinary tract, urinary and anal sphincters, and colon. SNM delivered by the Medtronic InterStim System is an advanced therapy option for the treatment of the indications specified in the clinical investigational plan. Safety and performance have been established with long-term follow-up reported in the literature.

This prospective clinical study will fulfill post-market clinical follow-up obligations for the InterStim Micro System and is an active mechanism to assess performance and safety in patients SNM therapy in an organized, systematic manner based on the intended use.

### 4.2. Purpose

The purpose of this investigation is to confirm long-term clinical performance and safety of the InterStim Micro System.

The primary objectives of the study will evaluate data at 3 months post-implant; however, subjects will be followed for 2 years for the [REDACTED] safety assessments.

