### Overactive Bladder Quality of Life Questionnaire (OAB-q)

The Overactive Bladder Quality of Life Questionnaire (OAB-q) is a 33-item validated questionnaire that was developed to assess symptom bother and the impact of overactive bladder (OAB) on health-related quality of life (HRQL). The questionnaire used in the current study includes a 4-week recall for symptom assessment. The questionnaire may also be used to drive health state utilities.

This questionnaire will be completed by the subject at Baseline, Three-month, Six-month, One-year, and Two-year Follow-up Visits.

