##### Medtronic Controlled Information

$H_a: \mu \neq 0$ 

Where  $\mu$  indicates the mean change in OAB-q HRQL total score from baseline to 3 months post-implant.

The power calculations were performed using PASS 11 statistical software. Based on the results of HRQL in OAB-q at 3 months post-implant reported in the InSite study, a mean score change of 30 at 3 months from baseline with the standard deviation of 27 are the assumptions used for the power calculation for this study. At an alpha level of 0.05, a sample size of 50 evaluable subjects results a power greater than 90% for this cohort.

The HRQL module and its subscales for International Consultation on Incontinence Questionnaire (ICIQ)-OABqol and OAB-q questionnaires are the same measures.

The attrition between implant and the primary endpoint at the 3-month Follow-up Visit is expected to be less than 10%. To accommodate attritions between implant and 3-month Follow-up Visit as well as during long-term follow-up, approximately 60 subjects will be implanted for this cohort. Based on historical Medtronic sponsored SNM studies (InSite study and SNS bowel), attrition at 2 year long-term follow-up visits is typically around 20%. Therefore, we expect attrition in this post-market study to be similar. In all cases of missing data, the reason will be collected and sensitivity analyses will be performed to evaluate the impact of missing data on primary objective.

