#### **Adjustment for Multiple Endpoints**

Adjustment for multiple endpoints is not required as the study focuses on three independent and different cohorts with independent endpoints and cutoff times. There is only one primary objective within each cohort.

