#### **Analysis Population**

The analysis on the primary outcome parameter and for the additional measures will be performed on subjects who provide complete data at baseline and 3 months (complete cases). For all primary objectives, a sensitivity analysis will be performed on imputed data using Multiple Imputation (MI) techniques. The details of MI will be described in the study SAP.

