#### Hypothesis

The null ( $H_0$ ) and alternative ( $H_1$ ) hypotheses are:

$$H_0: \mu = 0$$

$$H_1: \mu \neq 0$$

Where  $\mu$  indicates the mean change in OAB-q HRQL total score from baseline to 3 months post-implant.

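### The complete-case rules conflict and, read literally, exclude usable data from 6-month to 2-year analyses; a met primary objective supports a 3-month conclusion only

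*Protocol*

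**What the plan says.** **Purpose and time point.** The Protocol's title (Synopsis) calls the trial a "Post Market Clinical Follow-Up Study to Confirm Long-Term Outcomes". Section 4.2 says "The purpose of this investigation is to confirm long-term clinical performance and safety of the InterStim Micro System", and then "The primary objectives of the study will evaluate data at 3 months post-implant; however, subjects will be followed for 2 years for the", followed by redacted words and safety assessments. The OAB hypothesis (13.4.1) is on a parameter that "indicates the mean change in OAB-q HRQL total score from baseline to 3 months post-implant". The FI and NOUR hypotheses use the same time point, as do all power statements and minimum evaluable numbers. Protocol 13.1.3 adds: "There is only one primary objective within each cohort".

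**Data collected later.** For the OAB-q, Protocol 9.5 states: "This questionnaire will be completed by the subject at Baseline, Three-month, Six-month, One-year, and Two-year Follow-up Visits". It says the same for the CCIS. The NOUR diary is completed before each follow-up visit (9.1).

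**Who is analysed.** Four readable rules bear on this:
- Protocol 13.1.3, Analysis Population: the analysis of the primary parameter and "for the additional measures will be performed on subjects who provide complete data at baseline and 3 months (complete cases").
- SAP 7.1.3: the complete-case set is implanted subjects with data at baseline and at each follow-up visit.
- SAP 7.4, primary objective: complete means having data at the visits the analysis uses, here baseline and 3 months.
- SAP 7.4, diaries: a subject with at least one full 24-hour period at a visit counts for that visit.

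**Attrition.** Protocol 13.1.1 expects less than 10% loss by 3 months and says that "attrition at 2 year long-term follow-up visits is typically around 20" per cent. Subjects whose device is permanently explanted are exited (Protocol 6).

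**The concern.** The stated purpose is long-term, but the only readable formal test in each cohort is at month 3. Rejecting zero mean change at 3 months says nothing about 2 years. What the trial can say about lasting performance therefore rests on the later-visit estimates, and the readable text does not settle which subjects enter them.

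The choice of rule is not neutral. A rule requiring every visit keeps the subjects who stayed and complied. Protocol 9.9 names lack of efficacy and discomfort as examples of withdrawal reasons, and explanted subjects leave the study. Conditioning on complete attendance is therefore likely to favour subjects who did well. Applied to the primary analysis, it would select the 3-month set on events that happen after month 3. Protocol 6.2 says the performance data may be used to support claims, so this should be fixed before analysis.

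**Working it through.** **1. The plan's own power figures.** Two-sided one-sample t-test, alpha 0.05, noncentrality = (mean change / SD) × √n:
- OAB, n = 50, 30/27: above 99.99%.
- FI, n = 50, 5/6.2 (13.1.1) or 5/6 (Synopsis): 99.99%.
- NOUR, n = 30, 2/3: 94.2%.

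All reproduce the stated figure of greater than 90%.

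**2. The rules applied to three example subjects.** All three have baseline data.

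| Subject | Analysis | Protocol 13.1.3 | SAP 7.1.3, literal | Baseline and visit analysed |
|---|---|---|---|---|
| A: missed month 3, attended the other visits | 2 years | out | out | in |
| B: missed month 6 only | 2 years | in | out | in |
| B | 3 months (primary) | in | out | in |
| C: attended month 3, left before 2 years | 3 months (primary) | in | out | in |

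Protocol 13.1.3 drops A from the 2-year analysis although A has the data it needs. SAP 7.1.3 drops A and B. It also removes B and C from the 3-month primary analysis, against SAP 7.4.

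**3. Size of the literal SAP 7.1.3 set.** Subjects with every visit cannot outnumber those still followed at 2 years. Planned implants are 60/60/40 (OAB/FI/NOUR).
- 3-month data, at the 10% attrition bound: 60 × 0.9 = 54, 54, and 40 × 0.9 = 36.
- Every visit, at 20% attrition: at most 60 × 0.8 = 48, 48, and 40 × 0.8 = 32.
- Stated minimum evaluable: 50, 50, 30.

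OAB and FI fall 2 short and NOUR stays 2 above. The ceiling drops below the minimum once 2-year attrition exceeds (60 − 50)/60 = 16.7% for OAB and FI, or (40 − 30)/40 = 25% for NOUR. If attrition were 30% (an assumption), the ceilings would be 42/42/28. Missed intermediate visits lower all of these further, but the documents give no rate for them.

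**4. Is power the problem?** No. At 48/48/32 with the planned effects, power is above 99.9%, above 99.9% and 95.5%. The problem is which subjects are selected, and that the set contradicts the stated minimum.

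**5. What 2-year estimates could show.** With baseline and 2-year data on 48/48/32 and the planned SDs (assumed to hold at 2 years), the 95% CI half-width is t × SD/√n:
- OAB: 2.012 × 27/√48 = 7.8 points.
- FI: 2.012 × 6/√48 = 1.7 points, or 1.8 with SD 6.2.
- NOUR: 2.040 × 3/√32 = 1.1 CISC/day.

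These are narrow enough for a useful description against planned changes of 30, 5 and 2.

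**The case against.** **The additional measures are redacted.** They are blacked out in both documents, as are the words before the safety assessments in 4.2. SAP 8 contemplates p-values or confidence intervals on additional measures. A reader might infer that the plan has no 2-year performance analysis or test. The documents do not support that, because redacted text is not missing text. This stands, and no such absence is claimed.

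**The plan never says a 3-month success confirms long-term performance.** Section 4.2 openly separates the two, and the Synopsis design statement and SAP 7.2 use softer verbs. A short-term primary with descriptive follow-up is a legitimate design for a single-arm post-market study. This also stands. The request is only to state the limit of the conclusion.

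**Protocol 13.1.3 says who is analysed, not when.** Correct: it does not confine the additional measures to month 3. It does make month-3 data a condition of entry to later analyses.

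**The SAP can be read sensibly.** SAP 7.4 and the sections on determination of subjects under 7.9 point to baseline plus 3 months for the primary analysis, and the planned imputation analysis covers all implanted subjects. For the primary this largely answers the literal reading of 7.1.3, although the formal definition still says otherwise. For later visits, only the diary rule is visit-specific in readable text.

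**A gated 2-year test would be stronger.** Not clearly. If half the planned benefit were lost, a test of zero mean change would still pass with probability 96.5% (OAB), 78–81% (FI) and 44.7% (NOUR), and it would be run among subjects who kept the device. Such a test is optional.

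**Conclusion.** The point holds as a conflict of definitions with a real effect on who is analysed. For any 6-month to 2-year analysis, Protocol 13.1.3 excludes subjects who missed month 3, and SAP 7.1.3 excludes subjects who missed any visit, even when baseline and the visit in question are present. Both conflict with the visit-specific approach in SAP 7.4. Read literally, SAP 7.1.3 also caps the 3-month primary set at about 48/48/32, under the minimum of 50 for OAB and FI. That cap assumes 60/60/40 implants and 20% attrition at 2 years.

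The number lost to the month-3 rule cannot be estimated. A reader might apply the under-10% figure in Protocol 13.1.1, but that is attrition by month 3, not subjects who miss month 3 and return, and the documents give no rate for the latter.

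Every readable hypothesis and power statement is at 3 months, so a met primary objective supports a 3-month conclusion only. The 3-month test itself remains valid and well powered.

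**What to change.** 1. In Protocol 13.1.3 and SAP 7.1.3, define complete cases separately for each analysis: implanted subjects with data at baseline and at the visit analysed. Align SAP 7.4 and 7.9 with that definition and keep the diary rule as its diary version. Changing only one document would leave the conflict in place.
2. State in both documents that a met primary objective supports a conclusion about 3 months.
3. State that long-term performance will be described from the 2-year change in OAB-q HRQL, CCIS and CISC per day, with 95% CIs. Beside each estimate, report how many subjects were analysed and how many had exited after permanent explant. If the redacted measures already do this, a cross-reference is enough.

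The cost is wording: no added visits, data or subjects. If the sponsor regards the change as a principal feature, Protocol 13.1 and 15.12 require an amendment with IRB/EC submission. Otherwise it can be made in the SAP and justified in the clinical study report. It should be settled before data analysis begins.
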